Research question: does an enhanced diagnostic workup for patients about to start empiric tuberculosis treatment in Lusaka, Zambia, lead to alternative diagnoses and improved patient outcomes after six months?

Primary objective: to determine in what proportion of patients who are about to start empiric tuberculosis treatment, an alternative diagnosis can be made through the use of a concise additional workup by an experienced pulmonary physician, including review of available data, as well as additional laboratory, functional, and imaging investigations

Secondary objectives: to determine whether establishing and treating alternative diagnoses in patients who were about to start empiric tuberculosis treatment leads to improved quality of life and survival after six months

In- and exclusion criteria: All adult patients who have a negative initial GeneXpert MTB/RIF test on sputum, but are about to start standard first-line treatment for suspected pulmonary tuberculosis on clinical grounds (i.e. empiric tuberculosis treatment), at four first-level Hospitals in Lusaka, Zambia. Patients will be excluded if they are inpatients (due to suspected tuberculosis).

Number of eligible patients per year: Estimated 410 eligible patients per year in Chawama (450 clinically diagnosed pulmonary tuberculosis patients at Chawama first-level hospital in 2023, including children). The total population at Chawama first-level hospital in 2023 included 5361 presumptive tuberculosis cases, of whom 5270 had GeneXpert MTB/RIF testing done, and of whom 426 had a positive result from GeneXpert MTB/RIF. There is a discrepancy with the number of bacteriologically confirmed tuberculosis cases, which is reported at 663 for the year. The reason for this is not entirely clear, but might be due to additional testing being performed at different facilities, and the use of other tests for diagnosing tuberculosis, such as lipoarabinomannan assay and acid-fast bacilli smear. Interestingly, the percentage of patients who had a tuberculosis relapse was higher in patients being treated empirically than in patients with bacteriologically confirmed tuberculosis (107 out of 450 (24%) versus 107 out of 663 (16%)).

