Treatment outcomes for 2022 are as follows: 618 bacteriologically confirmed new cases of which 523 were cured (85%), 29 completed treatment, 36 died (6%), 3 failed treatment, 24 were lost to follow up, and 3 were not evaluated; 123 bacteriologically confirmed tuberculosis relapses of which 115 were

cured (93%), 5 died (4%), 2 were lost to follow up, and 1 was not evaluated; 352 clinically diagnosed new cases of which 308 completed treatment (88%), 35 died (10%), 1 failed treatment, 7 were lost to follow up, and 1 was not evaluated; 156 clinically diagnosed tuberculosis relapses of which 143 completed treatment (92%), 9 died (6%), and 3 were lost to follow up.

The other first-level hospitals had somewhat lower numbers of patients in 2023.

Intervention: All included patients will undergo the study intervention. Participants will be included from the tuberculosis clinic at first-level hospitals. They will be reviewed by one of the study physicians prior to initiating empiric tuberculosis treatment. A full history and physical examination will be taken and available results will be reviewed (laboratory results, sputum results, and chest X-ray). Depending on the results, appropriate measures will be taken there, including possible treatment with antibiotics or a wait-and-see approach for suspected viral infections. If further diagnostics are deemed to be indicated, a patient will be referred to the pulmonology clinic at University Teaching Hospital in Lusaka, Zambia. There, appropriate additional diagnostics will be requested, including additional blood tests (such as aspergillus serology), repeat chest X-ray, spirometry, CT-scan of the chest (if no other clear clinical diagnosis), bronchoscopy (if indicated based on CT-scan) and sputum and/or bronchial washing bacterial and mycobacterial cultures. The empiric treatment will be withheld initially if the study investigator thinks that an alternative diagnosis is more likely, while awaiting the additional investigations. If the study investigator thinks it is in the interest of the patient, then empiric tuberculosis treatment will be initiated while awaiting the results for the additional investigations. When a final diagnosis is made, appropriate treatment decisions will be made. If a clear diagnosis cannot be made locally, patients will be discussed in a multidisciplinary team meeting between St. Antonius Hospital and University Teaching Hospital.

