Statistical analysis: Descriptive statistics will be used to describe percentage of alternative diagnoses, as well as percentage of patients that has quality of life scores indicating they are not satisfied or very dissatisfied, the percentage of patients who received tuberculosis treatment and the percentage of patients that had side effects attributed to tuberculosis treatment. Paired analyses will be used to compare quality of life at baseline and during follow up. Multivariate regression analyses will be used to identify what factors associate with quality of life and survival. We will use per-protocol analysis methods for the primary analyses, with intention-to-treat analyses as a secondary tool. We will use a historic control group of patients who underwent empiric TB treatment at the study sites in the year prior to the study as a comparison for survival. Additionally, as data for the tuberculosis clinic are collected in a standard fashion, it will be able to compare the number of patients being referred to the clinic, the number of patients receiving treatment for bacteriologically confirmed tuberculosis, and the number of patients receiving empiric tuberculosis treatment, as well as treatment outcome data, between the study period and the period prior to and after the study.

Burden and risks for participants: The burden for the participants consists of having to travel to University Teaching Hospital (4.2 km – 10.6 km distance) for review and potential additional investigations that cannot be done on the same day (CT-scan and bronchoscopy). The additional investigations might necessitate venepuncture (slightly painful, low risk of hematoma or bleeding), chest X-ray (low dose radiation (0.1mSv)), spirometry (low risk of feeling uncomfortable), and

potentially CT-scan of the chest (medium dose radiation (6.1 mSv)), and bronchoscopy (discomfort for most patients, risk of serious complications (e.g. bleeding, pulmonary oedema, pneumothorax) ca. 1%). It needs to be emphasized that these investigations would be considered as the standard-of-care in a high-resource setting, and, in that sense, are not actually an additional burden at all.

Study duration: 16 months

Start date: 1/12/2024

Final inclusion: 31/12/2025

End date: 30/06/2026

Dissemination plan:

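### The plan asks whether the work-up and alternative diagnoses improve quality of life, but has no quality-of-life comparison group, no pre-specified contrast by diagnosis, and no rule for deaths or missing scores

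*Combined protocol and SAP*

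**What the plan says.** All places are in the combined protocol and SAP.

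- **Research question:** whether the work-up will "lead to alternative diagnoses and improved patient outcomes after six months".
- **Secondary objectives:** whether establishing and treating alternative diagnoses "leads to improved quality of life and survival after six months".
- **Intervention:** "All included patients will undergo the study intervention". There is no concurrent control.
- **Methods and Secondary outcomes:** EUROHIS-QOL is measured in participants at baseline and during follow-up. The outcomes are the 6-month score and the change from baseline to 6 months.
- **Statistical analysis, quality of life:** three analyses are planned. One is the "percentage of patients that has quality of life scores indicating they are not satisfied or very dissatisfied". The second is paired: "Paired analyses will be used to compare quality of life at baseline and during follow up". The third is a regression: "Multivariate regression analyses will be used to identify what factors associate with quality of life and survival".
- **Statistical analysis, comparators:** the historic control consists of empirically treated patients "at the study sites in the year prior to the study as a comparison for survival". Routine clinic data give patient numbers, "as well as treatment outcome data, between the study period and the period prior to and after the study". Neither is said to include quality of life.
- **Statistical analysis, analysis sets:** per-protocol and intention-to-treat analyses are named, but the sets are not defined. No section says how a death or a missing score is handled.

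**The concern.** The question and the objective are causal, while the quality-of-life data come from one group that all received the work-up. Patients enter when they are ill enough for a clinician to want to treat them, so some improvement by 6 months is foreseeable without any effect of the work-up. Background and justification itself expects that some have a self-limiting illness. Others will improve on whatever treatment they receive. A significant before-after improvement is therefore compatible with no effect of the work-up, and with no benefit from finding an alternative diagnosis.

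The paired change also needs two scores, so it leaves out patients who die and patients who are not reached. The worst outcome is then absent from the quality-of-life result.

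What is at stake is the conclusion. The protocol's section on other relevance says that positive findings will justify further building of specialty services, and an uncontrolled improvement could be cited for that.

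**Working it through.** **1. The plan's own figure.** Sample size calculation gives 238, inflated to about 300. It follows from a one-sample test of 5% mortality against a fixed 10%, two-sided alpha 0.05, power 80%:

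n = (1.960·√(0.10·0.90) + 0.842·√(0.05·0.95))² / 0.05² = 238.03, and 238/0.80 = 297.5, so about 300.

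The figure reproduces, but it rests on mortality. No sample size, SD or expected change is given for quality of life.

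**2. Which planned analysis could answer the causal question?**

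- Paired change: no comparison group.
- Percentage dissatisfied: no comparison group.
- Historic control: survival only.
- Routine clinic data: patient numbers and treatment outcomes only.
- Regression: names no exposure and no adjustment set. If final diagnosis were entered, it would compare people with different diseases, not the same people with and without the work-up.

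None of them can.

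**3. Number of pairs.** Inputs: 300 enrolled and deaths of 5% or 10% (Sample size calculation). Missing scores among survivors are an assumption, from none up to the whole 20% margin.

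- Most pairs: 300 × 0.95 = 285.
- Fewest pairs: 300 × 0.90 × 0.80 = 216.

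**4. Chance of a significant improvement when the work-up has no effect.** Let d be the background change in SD of the change (assumption). The chance is approximately Φ(d√n − 1.96).

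| d | n = 216 | n = 285 |
|---|---|---|
| 0 | 2.5% | 2.5% |
| 0.1 | 31% | 39% |
| 0.2 | 84% | 92% |
| 0.3 | 99.3% | 99.9% |

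Example: d = 0.2, n = 216 gives Φ(0.2 × 14.70 − 1.96) = Φ(0.98) = 0.84. More complete follow-up raises the chance; it does not help interpretation.

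**5. Deaths.** Let u be the dissatisfied share among survivors (assumption). Counting deaths as unfavourable in all 300:

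- 5% mortality: (15 + 285u)/300 = 24%, 43%, 62% for u = 20%, 40%, 60%. The shift is 4, 3 and 2 points.
- 10% mortality: (30 + 270u)/300 = 28%, 46%, 64%. The shift is 8, 6 and 4 points.

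**6. Missing scores.** The distance between counting all missing as favourable and all as unfavourable is (number missing)/300.

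- Low scenario: loss to follow-up in clinically diagnosed patients in 2022 was 7/352 = 2.0% (new) and 3/156 = 1.9% (relapse), reported under Number of eligible patients per year. Two per cent of 285 is about 6, and 6/300 = 2 points. For u = 40% at 5% mortality the bounds are (15 + 0.4 × 279)/300 = 42% and (15 + 0.4 × 279 + 6)/300 = 44%.
- Upper limit: the whole 20% margin as missing scores. At 5% mortality, 57/300 = 19 points; at 10%, 54/300 = 18 points.

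**The case against.** **The plan does compare quality of life.** A reader might infer that it contains no such comparison at all. The documents do not support that: there is a within-patient comparison and a regression. What is absent is a comparison group and a named contrast by diagnosis. This objection limits the wording; it does not remove the gap.

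**The time point is given.** One might say that the dissatisfied percentage has no time point. Statistical analysis does not repeat one, but Secondary outcomes lists quality of life at 6 months, which is its natural source.

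**The diagnosis is not known only at 6 months.** It is tempting to dismiss the regression because the final diagnosis comes from the 6-month file review. Intervention, however, describes treatment decisions once a diagnosis is reached during the work-up. Confounding by disease is the sound argument; timing adds little.

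**Missing data may be slight.** The 20% margin includes refusal, and people who refuse are never enrolled. The clinic's own loss was about 2%. This stands: 18-19 points is an upper limit. Quality-of-life scores may be missed more often than treatment outcomes, so 2% is a low scenario.

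**The death shift is modest and survival is reported separately.** This also stands, and it is one reason not to rate the point higher.

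**The percentages in step 4 are simply power for an assumed change.** Correct. They show the logic and are not a forecast for this trial.

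**Conclusion.** The concern holds in this form: the causal question about quality of life cannot be answered by the planned analyses, and no rule covers deaths or missing scores. The paired comparison remains a valid description of change in survivors with both scores.

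On size, a background improvement of 0.1 to 0.3 SD would produce a significant result with no work-up effect in roughly a third to nearly all trials. That range is an assumption, because the documents give no SD or expected change. With no background change the chance is the nominal 2.5%. Deaths move the dissatisfied percentage by 2-8 points, given 5-10% mortality and an assumed 20-60% dissatisfied among survivors. Missing scores add bounds from about 2 points wide to at most 18-19.

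A reader might go further and infer that the work-up does not improve quality of life, or that a positive finding would be false. The documents support neither; they show only that this design cannot tell. Quality of life is a secondary outcome, so the change should be made but is not critical to the trial.

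**What to change.** Make these changes before 6-month data are seen.

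1. **Research question and Secondary objectives.** Separate quality of life from survival in the secondary objective, and state it as a description of change from baseline to 6 months with a 95% confidence interval. The research question speaks only of patient outcomes in general, so add that it carries no causal claim for quality of life. Word the conclusion in the same way.
2. **Statistical analysis, deaths.** Label the paired change as survivors with both scores. Beside it, report the 6-month percentage among all enrolled patients, with known deaths counted as unfavourable. This is a new composite (dissatisfied or dead) and should be called an added supportive summary.
3. **Statistical analysis, missing scores.** Report the number of missing scores by vital status (known alive or unknown). Give the all-enrolled percentage with all missing counted as unfavourable, then all as favourable.
4. **Statistical analysis, regression.** Model the 6-month score adjusted for the baseline score, which is already collected. Report any diagnosis term as an association only.

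The cost is a short amendment to the objectives, a few lines in Statistical analysis and slightly more analysis work, with no new patients or data. The downside is a weaker quality-of-life claim. Items 2 and 3 deal with deaths and missing scores; they do not replace the missing comparator, which is why item 1 narrows the claim.

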Methods: Participants will be asked to participate in the study once the clinician at the first-level hospital has decided to start empiric tuberculosis treatment. If the patients provide written informed consent, they will be reviewed by the study physician on-site, and possibly referred for further investigations as described above. Quality of life will be assessed at baseline, as well as during follow up. Patients will be followed up for 6 months, at which time every patient file will be reviewed by a study investigator and the final diagnosis will be determined.

Primary outcome: diagnosis at 6 months (tuberculosis versus alternative diagnosis)

Secondary outcomes: quality of life at 6 months (EUROHIS-QOL), change in quality of life from baseline to 6 months (EUROHIS-QOL), survival at 6 months, number of patients that received tuberculosis treatment, number of patients that had side effects attributed to tuberculosis treatment,

Number of patients to include: 300

Sample size calculation: The power is set at 80% and α at 0.05. Assuming a 10% mortality in the historic control group (based on 2022 tuberculosis outcome data from Chawama first-level hospital), and a 5% mortality in the intervention group, 238 patients will have to be included. A safety margin of 20% of refusal to participate in the study and loss to follow up is assumed, so that approximately 300 patients will have to be included.

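### The survival objective points to a diagnosis settled only at six months, and the survival regression is not limited to variables known at enrolment; used as a fixed covariate, that diagnosis would bias the result

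*Combined protocol and SAP*

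**What the plan says.** Under Secondary objectives, the combined protocol and SAP puts the question "whether establishing and treating alternative diagnoses in patients who were about to start empiric tuberculosis treatment leads to improved quality of life and survival", with six months as the time point. The exposure in that sentence is the alternative diagnosis and its treatment.

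Under Methods, patients are followed for six months, and then "every patient file will be reviewed by a study investigator and the final diagnosis will be determined". The primary outcome is binary, tuberculosis or alternative diagnosis. Among the secondary outcomes is "survival at 6 months", so label and survival are fixed at the same time.

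The Statistical analysis section has two tools for survival:

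- Regression: "Multivariate regression analyses will be used to identify what factors associate with quality of life and survival". It gives no covariates, model type or time origin, and no rule for patients who die before the work-up is complete.
- An external comparison: "We will use a historic control group of patients who underwent empiric TB treatment at the study sites", from the year before the study. This compares whole groups and does not use the final diagnosis.

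Under Intervention, every included patient receives the work-up, so there is no concurrent group without it. The Research question is put at the level of the work-up: does offering it lead to alternative diagnoses and better outcomes?

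**The concern.** The historic comparison can speak to the work-up as a policy. It cannot separate out the effect of reaching an alternative diagnosis. The only within-cohort survival analysis is the factor regression, and final diagnosis is the factor that the secondary objective points to.

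That factor comes after baseline. A patient whose alternative diagnosis depends on referral, CT, bronchoscopy or culture must survive long enough for it to be made. Patients enter because a clinician has already decided to treat for tuberculosis, and the outcome has no undetermined class, so a patient who dies mid-work-up has to be put in one of two groups by a rule that is not stated. The person assigning the label can also know whether the patient died. Treatment received shares the timing problem, and the investigator chooses it on clinical judgement, so prognosis may enter as well.

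At stake is the reading of a secondary objective. Under Other relevance, positive findings are meant to justify further specialty services. An association produced by the timing of the label could be taken as evidence that the diagnosis itself saved lives.

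**Working it through.** **1. The plan's own figure.** Sample size calculation gives 10% against 5% mortality, power 80%, α 0.05 and 238 patients. A one-sample test against a fixed 10%, two-sided, gives

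n = (1.960·√(0.10·0.90) + 0.842·√(0.05·0.95))² / 0.05² = 238.03.

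With the 20% margin, 238/0.80 = 297.5, or 298, which agrees with approximately 300. This calculation concerns the historic-control comparison and is not affected by the present point.

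**2. Expected deaths.** From 0.05 × 238 = 11.9 to 0.10 × 300 = 30, so about 12 to 30.

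**3. Illustration with no true difference.** Assumed: 300 patients, 60% with a true alternative diagnosis, 5% mortality in both groups. That gives 9/180 deaths with an alternative diagnosis and 6/120 with tuberculosis. Let a fraction f of the 9 deaths be labelled tuberculosis because the work-up was unfinished.

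- f = 0: 9/180 = 5.0% and 6/120 = 5.0%, odds ratio 1.
- f = 1/3 (3 deaths moved): alternative 6/177 = 3.4%, tuberculosis 9/123 = 7.3%. Odds ratio, tuberculosis against alternative, (9/114)/(6/171) = 2.25.
- f = 1/2 (4.5 moved): 4.5/175.5 = 2.6% and 10.5/124.5 = 8.4%. Odds ratio (10.5/114)/(4.5/171) = 3.5.

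In general, with s the true share of alternative diagnoses, OR = (1 + f·s/(1−s))/(1−f). Overall mortality cancels. The documents give 45% (the retrospective study from Pakistan, Literature review) and 60–80% (Background and justification, midpoint 70%). At f = 1/3 the odds ratio is 1.91 for s = 45% and 2.67 for s = 70%. The value of f is an assumption throughout.

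**4. The opposite error.** If two tuberculosis deaths are instead reread as alternative diagnoses, the same cohort gives 11/182 = 6.0% against 4/118 = 3.4%, odds ratio (4/114)/(11/171) = 0.55. The direction is not fixed.

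**5. Simulation in terms of diagnostic delay.** No true effect, one million patients per scenario, mortality 5% or 10%, s = 45% or 70%. Assumed, not in the documents: exponential time to diagnosis; constant or front-loaded hazard (Weibull shape 0.6); deaths before diagnosis left in the comparison group. The entries are risk ratios for alternative diagnosis against the rest (truth 1.00; below 1 corresponds to an odds ratio above 1 in step 3), at 5% mortality:

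| Mean delay (months) | Constant, s 45% | Constant, s 70% | Front-loaded, s 45% | Front-loaded, s 70% |
|---|---|---|---|---|
| 0.25 | 0.93 | 0.88 | 0.80 | 0.67 |
| 1 | 0.75 | 0.62 | 0.56 | 0.43 |
| 2 | 0.61 | 0.48 | 0.45 | 0.33 |

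Across all scenarios, including 10% mortality, the range is 0.94 to 0.33.

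**6. Does the remedy work?** A two-month landmark, classifying survivors by their status on that date, returned 0.98 to 1.02. Splitting person-time at the diagnosis date returned 0.98 to 1.01 under constant hazard, but the crude ratio stayed at 0.67 to 0.85 under front-loaded hazard. A time-dependent covariate therefore belongs in a Cox model on time since enrolment. The simulation has no confounding by underlying disease, so it shows only that the timing problem is removed.

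**The case against.** A reader might infer that the bias is built into the plan, or that the regression will show better survival with an alternative diagnosis. The documents do not support either reading.

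- The Statistical analysis section never names diagnosis or treatment received as a covariate. The survival comparison that it describes, and on which the trial is sized, uses historic controls and not the label.
- Under Intervention, a study physician reviews every patient before treatment starts, and some alternatives can be settled on site. For those patients the delay may be close to zero.
- Every file is reviewed, which on its wording includes patients who died. No default to tuberculosis is stated.
- A label given with the outcome known can err either way (step 4). Case mix can also push either way: Background and justification lists both self-limiting viral infection and malignancy.
- In the one-third illustration the 95% interval for the odds ratio is 0.78 to 6.5 (log 2.25 = 0.811; standard error √(1/9 + 1/114 + 1/6 + 1/171) = 0.541), p = 0.13. That would not be proof of anything.

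All of this stands, and it makes the point conditional. It does not remove it. For referred patients the route can be long: CT and bronchoscopy cannot be done on the same day (Burden and risks for participants), and the existing videoconferences are bimonthly (Background and justification). Incomplete work-ups are realistic: 23 of 36 patients completed all investigations in the Tanzanian study in the Literature review. The objective as worded calls for the one covariate that is unsafe, and nothing in the plan rules it out.

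**Conclusion.** The concern holds in conditional form. If the six-month diagnosis, or treatment received, enters the survival regression as a fixed covariate, the estimate is open to immortal-time bias and to labelling informed by the outcome. The plan neither says that this will be done nor prevents it, and its secondary objective points that way.

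The possible size is material relative to 12 to 30 deaths: an odds ratio of 2.25 under the null if one third of alternative-diagnosis deaths are relabelled, and a risk ratio anywhere from 0.94 to 0.33 under the assumed delays. With short delays and constant hazard it is small (0.88 to 0.94). Size, and possibly direction, rest on the delay to diagnosis and on how unresolved deaths are classed, neither of which the documents give.

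The historic-control comparison and the sample size are not touched by this point. It concerns a secondary objective, and the change is worth making because it is cheap before analysis and diagnosis dates are best recorded prospectively.

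**What to change.** 1. **Secondary objectives.** Restate the survival objective as the effect of offering the enhanced work-up in all enrolled patients. This matches the Research question and the historic-control comparison on which the trial is sized.
2. **Statistical analysis.** Limit the survival regression to variables known at enrolment.
3. **If diagnosis is examined.** Record the date on which each diagnosis is established, and state how deaths before completion of the work-up are classed. Use a prespecified landmark (diagnosis as recorded on a fixed date, among patients alive then, with later survival as the outcome) or a time-dependent covariate in a Cox model on time since enrolment. Report deaths before the landmark separately. Present the result as exploratory association, because confounding by underlying disease remains.

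The cost is wording and one dated field. The landmark analysis discards the early deaths and, with so few in total, will be imprecise.

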There are several previous studies into alternative diagnoses in patients who were empirically treated for tuberculosis, but high-quality evidence is lacking. The only prospective study was done in Tanzania, and included 36 patients. Of these patients, 23 completed all additional investigations, and only 2 of these patients (6%) were confirmed to have tuberculosis. The other patients were diagnosed with pneumonia, bronchiectasis, interstitial lung disease, non-tuberculous pleural disease, malignancy, and chronic pulmonary aspergillosis.¹⁶ A retrospective study in Pakistan found that 45% of 61 patients who received empiric treatment later were found to have an alternative diagnosis, including malignancies, heart failure, chronic pulmonary aspergillosis, and bronchiectasis.¹⁷ In another study by the same authors, it was found that over a third of patients with allergic bronchopulmonary aspergillosis in a Pakistani tertiary care hospital, had initially been misdiagnosed as tuberculosis.¹⁸ In a study from Nigeria, it was found that a significant proportion of patients that were re-treated for tuberculosis, and had been classified as treatment failures, actually had chronic pulmonary aspergillosis.¹⁹ What complicates matters, is that pulmonary aspergillosis is frequently seen as a late complication of cavitary tuberculosis, even if the latter has been adequately treated.²⁰ A recent systematic review highlighted 80 cases in which various types of pulmonary fungal infections were initially misdiagnosed as tuberculosis.²¹ Furthermore, a study from South-Africa found that almost all patients who were treated for lymphoma at a tertiary level hospital, had received empiric tuberculosis treatment in the year prior.²² A study from Uganda found a lower, but still significant rate of 30% misdiagnosis of tuberculosis in patients with HIV-associated lymphoma.²³ A study from Malawi in a general oncology department found a misdiagnosis as tuberculosis in 1% of all referred patients.²⁴

Interestingly, in another study from Uganda, it was found that 88% of 162 patients who received a course of broad-spectrum antibiotics instead of empiric tuberculosis treatment, showed clinical improvement and 4% were treated for an alternative respiratory disease.²⁵

Type of research: prospective intervention study

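### The primary analysis is per-protocol, but the set is undefined; in this single-arm study with a conditional work-up, all enrolled patients fit the objective better

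*Combined protocol and SAP*

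**What the plan says.** The Statistical analysis section sets the order of the analysis sets: "We will use per-protocol analysis methods for the primary analyses, with intention-to-treat analyses as a secondary tool". Nothing in the document says what makes a patient per-protocol. There is no minimum work-up, no list of deviations, and no rule for a missed referral, unfinished tests, early death or loss to follow-up.

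Four other places bear on the point.

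- **Primary objective.** The target is the "proportion of patients who are about to start empiric tuberculosis treatment, an alternative diagnosis can be made through the use of a concise additional workup".
- **Intervention.** There is one arm: "All included patients will undergo the study intervention". The work-up is conditional. After the on-site review, "appropriate measures will be taken there, including possible treatment with antibiotics or a wait-and-see approach for suspected viral infections". Beyond that, "If further diagnostics are deemed to be indicated, a patient will be referred to the pulmonology clinic". CT and bronchoscopy carry further conditions.
- **Methods.** Consent comes before the study physician's review. At 6 months an investigator reviews every patient's file and assigns a final diagnosis.
- **Secondary outcomes, Sample size calculation and Statistical analysis.** Survival is a secondary outcome, but it drives the sample size (10% against 5% mortality, 238 patients, about 300 with the margin). It is compared with historic controls treated at the same sites.

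**The concern.** With one arm there is no crossover or allocation to respect. Refusers never enter any set, because consent comes first. Apart from patients enrolled in error, a per-protocol set can therefore only be all enrolled patients minus some who are removed for what happened after consent. Because the work-up is conditional, a patient settled on site with no further tests has followed the protocol, so completeness has no obvious meaning until it is written down.

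Two things are at stake. First, the headline proportion with an alternative diagnosis depends on an unstated rule, and that rule could be settled after diagnoses are known. Second, if 'primary analyses' includes survival, a patient who dies before the requested tests are done could be removed from the study group, while the historic group has no completion rule and keeps all its deaths.

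Non-completion is plausible. Tests may require travel and further visits, and the protocol reports of the one prospective study it cites: "Of these patients, 23 completed all additional investigations, and only 2 of these patients (6%) were confirmed to have tuberculosis". The printed 6% is 2/36; among the 23 completers it would be 2/23 = 8.7%. The choice of denominator already changes the figure there.

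**Working it through.** **1. The plan's own figure.** A one-sample test against a fixed 10%, two-sided alpha 0.05, power 80%:

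n = [(1.96 × √(0.10 × 0.90) + 0.84 × √(0.05 × 0.95)) / 0.05]² = 238.03

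238 / 0.80 = 297.5, or about 300. Both stated figures reproduce and are not in dispute. A two-sample formula does not give 238 (435 per arm, two-sided).

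**2. Two tenable meanings of per-protocol.**
- *On-site review done.* Nearly all enrolled patients qualify, so the effect is close to nil.
- *On-site review plus the tests requested for that patient.* Those who miss requested tests are dropped.

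**3. Effect on the primary outcome under the second meaning.** In general:

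per-protocol proportion − all-enrolled proportion = share dropped × (proportion in kept − proportion in dropped)

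Example; all shares are assumptions except the 300 enrolled:

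| Group | n | Alternative diagnosis |
|---|---|---|
| Settled on site | 100 | 90 (90%) |
| Referred, requested tests done | 150 | 90 (60%) |
| Referred, requested tests not done | 50 | 20 (40%) |

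- All enrolled: (90 + 90 + 20)/300 = 66.7%.
- Per-protocol: (90 + 90)/250 = 72.0%.
- Check: 50/300 × (72 − 40) = 5.3 points.

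If the 50 dropped patients were instead 90% alternative (45 of 50), all enrolled would be 225/300 = 75.0% and per-protocol still 72.0%, a shift of −3.0 points. The sign depends on who is dropped. With a 20-point gap and 2% dropped, the shift is only 0.4 points.

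**4. Effect on survival, if per-protocol governs it.** Let p be true mortality, f the share of deaths excluded and g the share of survivors excluded:

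per-protocol mortality = p(1−f) / [p(1−f) + (1−p)(1−g)]

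Inputs: p = 10% (the planned control rate; the 2022 Chawama data give 35/352 = 9.9% in new clinically diagnosed cases), no true effect, 300 enrolled. Controls are assumed at 450 to 1,800: 450 is Chawama's 2023 count of clinically diagnosed pulmonary cases, which includes children, and 1,800 is four sites of that size, although the other sites are said to be smaller. The test is a pooled two-sample z-test, two-sided 5%, with 400,000 simulated studies per case. This is not the test behind the 238.

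| Deaths excluded (f) | Survivors excluded (g) | Mortality | Result over 450-1,800 controls |
|---|---|---|---|
| 20% | 0% | 0.08/0.98 = 8.2% | false benefit 13-15% |
| 20% | 20% | 0.08/0.80 = 10.0% | false benefit about 2% |
| 10% | 20% | 0.09/0.81 = 11.1% | false harm 7-9% |

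The nominal rate in each direction is 2.5%. Equal shares give no bias.

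**5. What all-enrolled does to survival power, on the plan's one-sample test.**

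power = Φ[((0.10 − p₁)√n − 1.96 × 0.30) / √(p₁(1 − p₁))]

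- 240 completers at 5%: about 80%.
- Those 240 plus 60 non-completers at 10%: (12 + 6)/300 = 6%, power about 67%.
- All 300 at 5%: about 90%.

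**The case against.** The all-patient analysis is already planned as secondary, so no data are lost and a divergence would be visible. The primary outcome is analysed descriptively, so there is no test whose error rate could be inflated. The objective also speaks of diagnoses made by means of the work-up, which makes a proportion among patients who received it a defensible quantity. All of this stands. It narrows the point to a missing definition and to which result leads; it does not supply the definition.

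Three stronger readings are tempting, and the documents do not support them.

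- A reader might infer that per-protocol means completing the hospital referral work-up, which in the example above would give 90/150 = 60.0%. That conflicts with the Intervention section, under which a patient settled on site has received the intervention.
- A reader might infer that the set inflates the yield or favours the intervention on survival. No figure is given for who would be dropped, and patients who recover and skip tests would push mortality the other way.
- A reader might take the cited study's 13 of 36 not completing (36%) as the expected or greatest share dropped. It is one small study in another setting and bounds nothing here. The plan's 20% margin does not help, because it combines refusal before consent with later loss.

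**Conclusion.** The point holds and should be fixed; it does not invalidate the study. It is certain from the text that an undefined per-protocol set is primary, that it can essentially only remove consented patients for later events, and that the text does not say whether it covers survival. The objective and the file review of every patient make all enrolled the better-fitting primary set.

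Size and direction cannot be read from the documents. The effect is close to nil if per-protocol means that the on-site review was done. If requested tests are also required, it is about 5 points in the worked example, which rests on assumed shares. The survival figures depend on three things: per-protocol applying to survival, assumed exclusion shares, and a two-sample test with assumed control numbers. They show what an undefined rule permits, not what will happen.

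**What to change.** In the Statistical analysis section:

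1. Make all consented, eligible participants the primary set for diagnosis and for survival, counting every death from enrolment.
2. Report undetermined diagnoses as their own category within the all-enrolled denominator. The present two-way outcome leaves no place for them, whichever set is used.
3. Define per-protocol in advance as on-site review done plus the tests requested for that patient, state which outcomes it covers, and use it only as a sensitivity analysis.
4. Replace the intention-to-treat label with all enrolled participants, since nothing is randomised.

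The cost is a few sentences. No new data are needed and the planned 238 and 300 do not change. The headline yield may be lower. Survival power may also fall if non-completers die more often: about 67% for 300 patients at 6%, against 80% for 240 at 5%, on the plan's own test. That 80% would belong to a selected group. If non-completers have the same 5% mortality, keeping all 300 raises power to about 90%.
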